1 STUDY SYNOPSIS

Title:	A Post-market Clinical Follow-up Study to provide safety, performance and clinical benefits data on the Exceed ABT acetabular cup (implants and instruments) when used in combination with CoC or CoP bearing options.
CIP ID:	BMETEU.CR.EU37
Sponsor:	Zimmer GmbH
Manufacturer:	Biomet UK Ltd
Aim:	To collect survivorship and clinical outcomes long-term data confirming safety, performance and clinical benefits of the Exceed ABT cementless cup when used in combination with ceramic and polyethylene articulating liners.
Objectives:	
Primary Objectives:
 
Clinical performance - as measured by clinical score data (HHS, WOMAC and Oxford Hip Score), radiographic assessments and survivorship which will be based on removal of the device.
 
Secondary Objectives:
 
Safety will be evaluated by monitoring incidence of adverse events.

Indication/ Target Population:	
Indication:
 
1. Non- inflammatory degenerative joint disease including osteoarthritis, avascular necrosis & post – traumatic arthritis.2. Rheumatoid arthritis3. Correction of functional deformity4. Revision of failed joint reconstruction or treatment5. Treatment of femoral neck and trochanteric fractures of the proximal femur with femoral head involvement and which are unmanageable using other techniques. 
Population:
 
Male and Female ≥18 years

Inclusion/Exclusion Criteria	
Inclusion Criteria:
 
1. Patients who are capable of understanding the doctor's

	
explanations, following his instructions and are able to participate in the follow-up program
 
2. Patient who gave verbal consent to take part in the study at study commencement and written consent retrospectively at 10 years follow-up by signing the “GDPR Pa-tient Consent Form”
 
3. Age: => 18 years
 
4. Male and Female
 
5. Non- inflammatory degenerative joint disease including osteoarthritis, avascular ne-crosis & post – traumatic arthritis
 
6. Rheumatoid arthritis,
 
7. Correction of functional deformity
 
8. Revision of failed joint reconstruction or treatment
 
9. Treatment of femoral neck and trochanteric fractures of the proximal femur with femoral head involvement and which are unmanageable using other techniques

	
Exclusion Criteria:
 
1. Infection, sepsis, and osteomyelitis2. Patients who are unwilling or unable to give consent, or to comply with the follow-up program.3. The patient is known to be pregnant or breastfeeding4. Any vulnerable subjects (= individuals whose willingness to volunteer in a clinical investigation could be unduly influenced by the expectation, whether justified or not, of benefits associated with participation or of retaliatory response from senior members of a hierarchy in case of refusal to participate)5. Uncooperative patient or patient with neurologic disorders who are incapable of following instruction6. Osteoporosis7. Metabolic disorder which may impair bone formation8. Osteomalacia9. Local and distant foci of infection10. Rapid joint destruction, marked bone loss or bone resorption apparent on roentgenogram11. Vascular insufficiency, muscular atrophy, or neuromuscular disease12. Skeletal immaturity13. Morbid obesity

	
14. Foreign body sensitivity. Where suspected, material sensitivity tests are to be made prior to implantation.
 
15. Any condition that may interfere with the survival of the implant such as Paget's disease, Charcot's disease, sickle cell anaemia or traits, lower extremity muscular atrophy or neuro-muscular disease'

Study Design:	A single-center, cohort observational clinical outcomes study
Clinical Phase:	Post-market
Number of Subjects:	676
Length of Study:	13 years (3 years enrollment plus 10 years follow-up): Post-operative follow-up visits at: 1, 3, 5, 7 and 10 years. Start date: Nov. 2007
Study Device:	Exceed ABT Acetabular System - a multiple bearing option system (implants and instrumentation)
Scores:	Harris Hip Score, Womac Hip Score, Radiographic Assessment & Oxford Hip Score
Documentation:	Paper / Electronic

2 STATISTICAL ANALYSIS PLAN

2.1 Sample Size

This study is a non-comparative case-series, therefore no sample size determination was performed. The aim is to collect clinical outcomes data on the Exceed ABT cementless cup.

2.2 Statistical Analysis

Data collected in the study will be summarized descriptively. Descriptive summaries will be the basis of study reports.

Continuous data (e.g. age) will be summarized through means, medians, standard deviation, minimum, maximum and 95% confidence intervals (CIs) over time periods of interest. Categorical data (e.g. gender) will be summarized using counts, percentages and 95% confidence limits over time periods of interest. Summaries of implant-related revision rates and complication data will be presented as frequencies and percentages. Subgroup summaries will be generated as needed either by strata within the study population (e.g. male vs. female) or by different cut-points (e.g. body mass index (BMI) ranges). Patient confidentiality will be protected at all times, and patient identifiers will not be included in data summaries.

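### Survivorship is a primary 10-year measure, but the analysis section states no survivorship analysis; device failure is covered only by counts and percentages of implant-related revisions, with no denominator and no allowance for death or loss

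*Combined protocol and SAP*

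**What the plan says.** The Aim in the Study Synopsis is "To collect survivorship and clinical outcomes long-term data confirming safety, performance and clinical benefits". The Primary Objectives list clinical scores, radiographic assessments and "survivorship which will be based on removal of the device". The synopsis gives 676 subjects and schedules "Post-operative follow-up visits at: 1, 3, 5, 7 and 10 years".

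Section 2.2 is the whole of the analysis text. It is descriptive throughout. On device failure it says only that "Summaries of implant-related revision rates and complication data will be presented as frequencies and percentages". A general rule could also be applied to revisions: "Categorical data (e.g. gender) will be summarized using counts, percentages and 95% confidence limits over time periods of interest". Section 2.2 mentions neither survivorship nor any time-to-event estimate. It gives no time origin, no denominator for the percentages, and no treatment of death or loss to follow-up.

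Two other statements bear on the point. Section 2.1 says "This study is a non-comparative case-series, therefore no sample size determination was performed". One inclusion criterion in the synopsis requires verbal consent at the start and "written consent retrospectively at 10 years follow-up".

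**The concern.** Over 10 years, some patients in a hip cohort will die or be lost with the device still in place. A survivorship estimate has to say what happens to them; a bare percentage does not. Divided by everyone implanted, the percentage treats each lost patient as never having had a removal. Divided by removed patients plus those seen at 10 years, it drops patients who contributed years without removal.

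The event also needs settling. The primary objective counts removal of the device, while Section 2.2 counts revisions judged implant-related. A removal judged unrelated to the implant could count under one and not the other.

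No test or decision rule hangs on the result. But 10-year device failure is a main product of a study meant to confirm safety and performance. A reader given one percentage could not tell whether it is a net risk (the risk if nobody died or was lost), a cumulative incidence in the presence of death, or a proportion among those who stayed.

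**Working it through.** **Text check.** The Primary Objectives call for survivorship with device removal as the event. Section 2.2 has one sentence on revisions and one general rule for categorical data. The general rule can add 95% limits by time period, but it supplies no at-risk denominator and no censoring rule. The gap is therefore present on the text. The plan states no figure on this point that could be reproduced.

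**Illustration of size.** From the documents: N = 676 and a 10-year horizon, treating 676 as the number implanted. Assumed, because the documents give no rates: net 10-year removal of 5%, constant hazards, loss independent of failure, and two attrition patterns (death d and loss l per year).

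Let r = −ln(0.95)/10 = 0.00513 per year and s = r + d + l.

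- Removals observed, over all implanted: A = (r/s)(1 − exp(−10s))
- Share reaching 10 years with the device in place: E = exp(−10s)
- Removals over removed plus completers: C = A/(A + E)
- Cumulative incidence with death as a competing event: (r/(r + d))(1 − exp(−10(r + d)))
- Attrition: 1 − exp(−10(d + l))

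*d = l = 0.01.* s = 0.02513, E = 0.7778, A = (0.00513/0.02513)(1 − 0.7778) = 0.0454, C = 0.0454/(0.0454 + 0.7778) = 0.0551.

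*d = 0.03, l = 0.02.* s = 0.05513, E = 0.5762, A = (0.00513/0.05513)(1 − 0.5762) = 0.0394, C = 0.0394/(0.0394 + 0.5762) = 0.0640.

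| Quantity | 1% death, 1% loss | 3% death, 2% loss |
|---|---|---|
| Attrition over 10 years | 18% | 39% |
| Expected removed / lost / died, of 676 | 30.7 / 59.8 / 59.8 | 26.7 / 103.9 / 155.9 |
| Percentage over all implanted | 4.5% | 3.9% |
| Percentage over removed plus completers | 5.5% | 6.4% |
| Net risk (assumed) | 5.0% | 5.0% |
| Cumulative incidence | 4.8% | 4.3% |
| Coverage of a 95% Wilson interval, all implanted: net / cumulative incidence | 93% / 95% | 79% / 94% |

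In the heavier case the denominator alone moves the figure by 6.4 − 3.9 = 2.5 points, half of the assumed 5%. With net removal of 3% or 8% at the same attrition, the two percentages are 2.4% and 3.9%, or 6.3% and 10.2%.

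With death at 3% per year and no loss, the all-implanted percentage is 4.33%, exactly the cumulative incidence. Death alone therefore does not bias it against that target; loss does.

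**What Kaplan-Meier does and does not repair.** In simulation with independent loss (12,000 replicates), Kaplan-Meier covered net risk, and Aalen-Johansen covered cumulative incidence, about 95% of the time in both cases. If the removal hazard is instead three times higher after loss (an assumption for illustration only), true net removal is 5.5% at 1%/1% and 5.9% at 3%/2%. Kaplan-Meier still averages 5.0%, and its coverage falls to 94% and 89%.

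**Consent criterion.** If only patients who reach 10 years and then sign are analysed, nobody is censored before 10 years. Kaplan-Meier at 10 years then equals the crude percentage, and the choice of estimator changes nothing.

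**The case against.** The strongest reply is that Section 2.2 is silent on survivorship rather than wrong about it. Its revision sentence pairs revisions with complications and may be meant as safety reporting, for which counts and percentages are suitable. A Kaplan-Meier curve is itself descriptive, and nothing excludes it. This stands in part. A reader might infer that the sponsor has chosen crude percentages as its survivorship analysis; the documents do not say so. Nor is the difference between removal and implant-related revision necessarily a contradiction, since they may be two separate outputs. What remains is that a primary measure has no stated analysis, and the descriptive design does not excuse that: Section 2.1 uses the design to explain the missing sample size calculation, not a missing estimator.

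A second reply concerns size. Every rate above is assumed, and the 79% coverage arises only against net risk. Against cumulative incidence the all-implanted percentage performs at 94–95%. This stands, and it rules out saying that the crude percentage is badly wrong whatever the target.

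A third reply is that Kaplan-Meier is not always better. In the dependent-loss illustration, the completer percentage covers true net removal at 94.9% (1%/1%) and 91.5% (3%/2%), against 93.8% and 88.7% for Kaplan-Meier; with 2% loss and no death the figures are 94.4% and 87.3%. This is true, but it reflects errors that happen to offset. With independent loss the completer percentage covers net risk only 90% and 72% of the time. It is a reason to state the censoring assumption, not to leave the denominator open.

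Finally, 676 could be the consented cohort rather than everyone implanted. The documents do not settle this, and under that reading the illustration of attrition would not apply.

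**Conclusion.** The point holds as an omission that should be fixed. Survivorship is primary, and Section 2.2 gives no analysis for it; the one stated summary of device failure has no denominator and no allowance for death or loss. If failure is reported that way, the effect under the stated assumptions is modest at 18% attrition (4.5% or 5.5% against 5.0% net). It is material at 39% attrition if net risk is the target (3.9% or 6.4%), and small for the all-implanted figure if cumulative incidence is the target (3.9% against 4.3%). These figures assume constant hazards, independent loss and 676 implanted patients; the documents supply no removal, death or loss rate.

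Two stronger conclusions are not supported. The documents do not show that a biased figure will be reported. Nor would Kaplan-Meier remove every problem: it is too low if lost patients fail more often, and it cannot undo selection if only patients consenting at 10 years are analysed.

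**What to change.** Keep the existing sentence in Section 2.2 for complications and raw revision counts, state its denominator, and add wording such as:

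> Survivorship (time from implantation to device removal) will be estimated by Kaplan-Meier in all implanted patients, censoring at death or last contact, with 95% CI and numbers at risk at 1, 3, 5, 7 and 10 years. Cumulative incidence of removal, with death as a competing event, will be reported alongside.

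Then:

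- State whether device removal and implant-related revision are the same event or two separate outputs, and define each once.
- Note that Kaplan-Meier assumes censoring independent of failure. A sensitivity analysis for loss is optional.
- Report how many implanted patients died, were lost, or gave no written consent at 10 years, as far as consent permits use of their data. If the analysis is confined to those consenting at 10 years, say so and describe the selection, because no estimator corrects it.

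The cost is SAP wording and light programming. The analysis needs operation, removal, death and last-contact dates, which the documents do not show are recorded. The reported failure figure may be less favourable than the percentage over all implanted patients.

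### Does naming only implant-related revision rates in the SAP leave the survivorship event, device removal, without an analysis?

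*Combined protocol and SAP*

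**What the plan says.** The Primary Objectives in Section 1 (Study Synopsis) define clinical performance by three hip scores, radiographic assessment and "survivorship which will be based on removal of the device". No cause of removal is singled out or excluded. The Aim in the same section is "To collect survivorship and clinical outcomes long-term data confirming safety, performance and clinical benefits of the Exceed ABT cementless cup", with the liners described as what the cup is used with.

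The Study Device row of the synopsis is broader: "Exceed ABT Acetabular System - a multiple bearing option system (implants and instrumentation". Section 2.1 returns to the cup: "The aim is to collect clinical outcomes data on the Exceed ABT cementless cup".

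Section 2.2 opens with a general commitment: "Data collected in the study will be summarized descriptively". It then prescribes counts and percentages with 95% confidence limits for categorical data, by time period. On device failure it says: "Summaries of implant-related revision rates and complication data will be presented as frequencies and percentages". It does not define implant-related or revision, and it does not use the words survivorship or removal.

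**The concern.** The event in the primary objective and the event in the named SAP summary carry different labels, and nothing connects them. The difference could work in either direction.

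- **Narrower.** If implant-related is a judgement about cause, a device taken out for a reason judged unrelated to the implant is a removal but would not be counted.
- **Wider.** If revision includes operations that leave the device in place, events that are not removals would be counted.

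The word device adds a second uncertainty. An isolated liner exchange could be a removal if the device is the whole acetabular system, and not if it is the cup.

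Single-arm results make this look more serious. With no comparator, the absolute failure percentage is itself the result, and the definition of the numerator sets it. The study began in November 2007 and no blinding is described, so failures are visible as they occur. A loosely defined event could in principle be settled after the counts are known.

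**Working it through.** **There is no plan figure to reproduce.** Section 2.1 states that no sample size determination was made, and the documents give no removal or revision rate. The check is therefore a comparison of the texts, followed by an illustration.

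**Comparison of the texts**

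1. *Is the event defined anywhere?* Yes. The Primary Objectives name removal as the basis of survivorship. Section 2.2 does not replace that definition; it is silent on it.
2. *Does Section 2.2 reach removal data?* Yes, in general terms. Whether a device has been removed is a yes/no item. If it is recorded, it falls under both the opening commitment and the rule for categorical data, and both say what will be done, not what may be done.
3. *Do the two terms conflict?* Not demonstrably. Implant-related revision can be read as revision surgery involving the implant, as distinct from the complications named in the same sentence. Neither section describes any assessment of the cause of a revision, so the restrictive reading is possible but not stated.
4. *What is the device?* The title and Aim in the synopsis, and Section 2.1, all take the cup as the object of study. The title and Aim present the bearings or liners as used with it. The Study Device row includes instrumentation, which does not stay in the patient, so that row reads as a product description and not as an endpoint definition. The cup is the more natural reading, although the liner question is not expressly closed.

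**Illustration**

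Let d be the proportion with the device removed, s the share of removals classed as implant-related, and r the proportion with a counted revision that leaves the device in place.

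Reported proportion = s × d + r

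Gap against removal = r − (1 − s) × d

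Only N = 676 comes from the documents (synopsis, Number of Subjects); d, s and r are assumptions.

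With d = 5%, removals = 676 × 0.05 = 33.8:

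| s | r = 0 | Gap (points) | r = 2% (676 × 0.02 = 13.5) | Gap (points) |
|---|---|---|---|---|
| 1.00 | 33.8 events, 5.00% | 0 | 47.3 events, 7.00% | +2.00 |
| 0.75 | 25.4 events, 3.75% | −1.25 | 38.9 events, 5.75% | +0.75 |
| 0.50 | 16.9 events, 2.50% | −2.50 | 30.4 events, 4.50% | −0.50 |

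Varying d with r = 0, rounded to whole events:

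| d | Removals | s = 1.00 | s = 0.75 | s = 0.50 |
|---|---|---|---|---|
| 3% | 20 | 2.96% | 2.22% (15) | 1.48% (10) |
| 5% | 34 | 5.03% | 3.85% (26) | 2.51% (17) |
| 8% | 54 | 7.99% | 5.92% (40) | 3.99% (27) |

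At d = 5% and s = 0.50, the exact (Clopper-Pearson) 95% intervals are 3.51% to 6.96% for removal (34/676) and 1.47% to 4.00% for the narrower count (17/676).

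The gap is zero when s = 1 and r = 0, that is, when the terms coincide. Nothing in the documents favours any other row, and the range reflects the inputs chosen.

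**The case for a change.** The best case for a change is that a descriptive percentage still needs a defined numerator. A general promise to summarise the data does not designate removal as the survivorship result. The complication data named beside the revision rates fit the secondary safety objective ("Safety will be evaluated by monitoring incidence of adverse events") better than the primary one. One or two sentences and one table would align the labels, with no new patients or visits.

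Much of this is correct as description. The labels differ, implant-related revision is undefined, and the status of an isolated liner exchange is not spelled out. A sponsor who chose to add a sentence would do no harm.

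It does not follow that the stated event will go unanalysed. The synopsis supplies the definition and Section 2.2 supplies the obligation to tabulate. Worry about a definition chosen afterwards also has limited force. A report that offered only cause-restricted revisions as survivorship would depart from the synopsis, and a reader holding both sections could see that. Nor would it be safe to insist on removal for any reason as though the synopsis said so: it names no restriction, which makes all-cause the natural reading, but it does not use those words.

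**Conclusion.** No change to the plan is called for. This is a gap in terminology that analysts fill sensibly: report removal of the device as the survivorship event, as the synopsis requires, and show implant-related revisions as the further summary that Section 2.2 names. Where liner exchanges with the cup retained occur, the descriptive rules allow them to be listed separately, so a reader can count them either way.

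Under the assumed inputs in the 5% table, the reported figure could lie from 2.5 points below to 2.0 points above the removal percentage; at 8% removal with half classed as implant-related, the shortfall would be 7.99 − 3.99 = 4.0 points. These figures show sensitivity to a definition and are not evidence of error. The documents state no hypothesis, comparator, threshold or success criterion, so no stated decision turns on the difference.

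The conclusion rests on two assumptions: that removals are recorded at follow-up, and that the analysts read Section 2.2 together with the Primary Objectives. How death and loss to follow-up should be handled in a survivorship estimate is a separate question and is not settled here.

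### Section 2.2 does not say that revision and complication percentages carry confidence limits, so zero or rare events may be reported with no upper bound

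*Combined protocol and SAP*

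**What the plan says.** Section 2.2 (Statistical Analysis) sets its reporting rules in consecutive sentences.

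- Continuous data are summarised by "means, medians, standard deviation, minimum, maximum and 95% confidence intervals (CIs) over time periods of interest".
- For categorical data: "Categorical data (e.g. gender) will be summarized using counts, percentages and 95% confidence limits over time periods of interest".
- For revisions and complications: "Summaries of implant-related revision rates and complication data will be presented as frequencies and percentages".
- For subgroups: "Subgroup summaries will be generated as needed either by strata within the study population". No statistics are named for them.

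The synopsis (section 1) lists among the primary measures "survivorship which will be based on removal of the device". The secondary objective reads: "Safety will be evaluated by monitoring incidence of adverse events". The planned number is 676, and the follow-up schedule is "Post-operative follow-up visits at: 1, 3, 5, 7 and 10 years". Section 2.1 adds: "This study is a non-comparative case-series, therefore no sample size determination was performed".

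**The concern.** Two general rules with 95% limits are followed by a specific sentence without them. That sentence also drops the reference to time periods that both general rules carry. If the general categorical rule were meant to apply unchanged, a separate sentence would hardly be needed, so an analyst could reasonably take the specific one as complete.

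The study aims to confirm safety, has no comparator and no hypothesis test, and states no precision target for its 676 subjects. Section 2.2 makes descriptive summaries the basis of the reports, so no later inferential step would supply the missing uncertainty. In that setting the upper confidence limit is what tells a reader which event rate the data rule out. A zero count from 100 patients and a zero count from 676 give the same percentage but support different conclusions.

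**Working it through.** **Is there an interval elsewhere?** Section 2.2 is the only place that describes analysis, and section 2.1 gives no precision calculation. There is therefore no figure of the plan's own to reproduce. Outputs compared:

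| Output | 95% interval stated? |
|---|---|
| Continuous data | Yes |
| Categorical data | Yes |
| Revisions and complications | Not named |
| Survivorship (primary measure) | No estimator and no interval |
| Subgroup summaries | No statistics named |
| Adverse-event incidence | Not mentioned in section 2.2; covered only if the categorical rule is taken to apply |

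**Inputs.** n = 676 is from the synopsis. The 95% level is the one section 2.2 uses for other data. Event counts and smaller evaluable numbers are assumptions, because the documents give neither event rates nor loss to follow-up. 507 and 338 are 75% and 50% of 676; 200, 150 and 100 are illustrative.

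**Formulas.** Exact (Clopper-Pearson) two-sided 95% limits for x events in n patients:

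- lower = 0.025 quantile of Beta(x, n − x + 1), or 0 when x = 0
- upper = 0.975 quantile of Beta(x + 1, n − x)
- for x = 0 the upper limit reduces to 1 − 0.025^(1/n)

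**Zero events.**

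| n evaluable | 1 − 0.025^(1/n) |
|---|---|
| 676 | 0.54% |
| 507 (assumed) | 0.72% |
| 338 (assumed) | 1.09% |
| 200 (assumed) | 1.83% |
| 150 (assumed subgroup) | 2.43% |
| 100 (assumed) | 3.62% |

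All six rows would print as 0 (0%).

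**Few events, n = 676.**

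| Events (assumed) | Percentage | Exact 95% limits |
|---|---|---|
| 1 | 0.15% | 0.00% to 0.82% |
| 3 | 0.44% | 0.09% to 1.29% |
| 7 | 1.04% | 0.42% to 2.12% |
| 34 | 5.03% | 3.51% to 6.96% |

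**The method must be named.** The Wald interval is p ± 1.96·√(p(1 − p)/n). At x = 0 it collapses to 0 to 0, and at 3 of 676 its lower limit is negative (−0.06%). The Wilson upper limit at 0 of 676 is 0.57%, close to the exact 0.54%.

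**The denominator must be named.** Suppose 7 revisions are seen. With all 676 in the denominator the result is 1.04% (0.42% to 2.12%). If half the cohort had left before they could contribute an event, the relevant figure is 7 of 338, which is 2.07% (0.84% to 4.22%). Keeping all 676 would roughly halve both the estimate and its upper limit. Limits on a crude 10-year percentage are therefore not enough when patients are lost.

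**The case against.** The strongest reply is that whether a patient had a revision or a complication is categorical, gender is only an example in the general rule, and nothing in the specific sentence excludes limits. On that view the sentence adds to the general rule and does not replace it. This stands as far as it goes: a reader might infer that the plan deliberately sets a weaker standard for safety, and the text does not establish that. But the plan does not settle the question the other way either, and omitting the limits would comply with it.

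A reader might also infer that revisions and complications are the only results left without limits. The documents do not support this, since survivorship and the subgroup summaries have no stated interval.

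Nor does the sentence cover the whole safety objective. The synopsis defines safety by adverse-event incidence, which the sentence does not mention and which may fall under the categorical rule. Device removal belongs to survivorship, under the primary objective.

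Finally, counts will be reported, so a reader with the denominator can derive the limits, and no decision rule depends on them. This limits the harm, and it means that subgroup percentages would not be shown without any sign of their size. It does not remove the problem: no denominator is promised, and conclusions are usually drawn from what is printed.

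**Conclusion.** The point holds in a limited form. As written, section 2.2 allows implant-related revision and complication results to be reported without confidence limits, although it requires limits for other categorical data. This is a gap in specification and should be closed; it does not invalidate the study.

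The effect is modest if nearly everyone is evaluable: the unprinted upper limit at zero events is 0.54% with 676 patients. It grows to between 1.09% and 3.62% if 338 down to 100 are evaluable, as could arise late in a 10-year follow-up or in a subgroup. These evaluable numbers and all event counts are assumptions. The limits also assume that each patient in the denominator was fully observed for the period concerned.

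**What to change.** Replace the sentence on revisions and complications in section 2.2 with:

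> Implant-related revision and complication data, and adverse-event incidence, will be presented as number of patients with at least one event, number of events, percentage and exact (Clopper-Pearson) or Wilson two-sided 95% confidence limits, overall, by follow-up interval and in any subgroup, with the number of patients under observation in that interval as the stated denominator. The upper limit will be shown when no events occur. Cumulative revision over follow-up will be given with a 95% confidence interval from a time-to-event estimate that censors patients lost to follow-up.

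One of the two interval methods should be chosen before analysis. The intervals can follow the visit schedule: surgery to 1 year, then 1–3, 3–5, 5–7 and 7–10 years. The plan should also say how deaths are handled in the time-to-event estimate. The last sentence of the replacement gives cumulative revision a method and an interval, which the plan now lacks for survivorship.

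The cost is a short change to the SAP and minor programming. No new visits or measurements are needed, though patients' last-contact dates must be available for the censoring. The reported safety figures will look slightly less favourable, because their uncertainty will be visible.

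### Should section 2.2 name bearing type as a descriptive stratum, given that the title and aim name the bearings?

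*Combined protocol and SAP*

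**What the plan says.** The Study Synopsis mentions the bearings twice. The title speaks of the cup "when used in combination with CoC or CoP bearing options", and the aim speaks of it "when used in combination with ceramic and polyethylene articulating liners". Only the title uses the CoC and CoP abbreviations; the aim makes the same distinction in other words.

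The primary objectives do not divide the cohort. They list three hip scores and "radiographic assessments and survivorship which will be based on removal of the device", all for the device as such. The design is given as "A single-center, cohort observational clinical outcomes study". Section 2.1 states "This study is a non-comparative case-series" and restates the aim as collecting outcome data on the cementless cup, without mentioning a bearing.

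Section 2.2 is descriptive throughout. On subgroups it says "Subgroup summaries will be generated as needed either by strata within the study population (e.g. male vs. female", then gives BMI ranges as an example of cut-points. Neither 2.1 nor 2.2 refers to bearing or liner, and no part of the documents gives the number of patients per bearing.

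**The concern.** Bearing is the only division of the cohort that the title and aim point to, yet the plan does not commit to showing results by it. A report with no by-bearing table, or with one for selected outcomes only, would comply with section 2.2. A reader who wants to know how the cup did with each liner might then learn little about the less-used one.

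Timing sharpens the worry. Inclusion criterion 2 describes a "Patient who gave verbal consent to take part in the study at study commencement and written consent retrospectively at 10 years follow-up", which reads as text written after enrolment. If section 2.2 dates from the same time, the choice of which subgroups to show could be made with results in hand. What is at stake is completeness of description. There is no error rate to protect.

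**Working it through.** **1. No figure to reproduce.** The 676 subjects are stated without a derivation, and section 2.1 says that no sample size determination was made. Nothing in the plan is calculated by bearing.

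**2. Does the plan, followed as written, answer its objectives?** The objectives ask for hip scores, radiographic findings, survivorship and adverse events for the cup. Section 2.2 summarises the cohort as a whole. The target and the analysis are at the same level. The words about bearings in the title and aim can be read as the conditions under which the cup was used; neither place calls bearing a stratum.

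**3. Is a by-bearing summary excluded?** No. Section 2.2 allows strata within the study population and offers sex as an example. Bearing fits that clause as well as sex does, and no stratum, sex included, is committed to.

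**4. How much can a cup-level table leave open?** Let p be the overall removal proportion and s the share of the less-used bearing, with p no larger than s. That bearing's own proportion lies between 0 and p/s. The upper limit is 2p at s = 50%, 3.3p at 30%, 5p at 20% and 10p at 10%. It is reached only if every removal falls in that bearing, so it is a logical limit and not an expectation. It is the same for any unreported subgroup of that size, whether defined by sex, BMI or indication.

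**5. What would by-bearing tables show?** Assumptions, none of them in the documents: overall removal 5%, a twofold ratio with the higher rate in the less-used bearing, complete follow-up. The lower rate is 0.05/(1 − s + 2s) = 0.05/(1 + s), and the higher rate is twice that. Counts are rounded; intervals are exact 95%.

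| s | Lower-rate bearing | Higher-rate bearing |
|---|---|---|
| 50% | 3.33%: 11/338, 1.64–5.75% | 6.67%: 23/338, 4.36–10.04% |
| 20% | 4.17%: 23/541, 2.71–6.31% | 8.33%: 11/135, 4.14–14.11% |
| 10% | 4.55%: 28/608, 3.08–6.59% | 9.09%: 6/68, 3.31–18.22% |

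Overall, 34/676 gives 3.51–6.96%. The smaller group is imprecise. The paired intervals overlap, but that does not mean a difference could never be shown. For 11/338 against 23/338 the difference is 12/338 = 3.55 percentage points, with Wald 95% CI 0.27 to 6.83, chi-square p = 0.035 and Fisher p = 0.051. The sound reason for not comparing bearings is that this is an observational cohort, so any difference may reflect which patients received which liner.

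**6. Timing.** The synopsis gives "Post-operative follow-up visits at: 1, 3, 5, 7 and 10 years. Start date: Nov. 2007" and three years of enrolment. The last scheduled 7-year visits fall at Nov 2007 + 3 + 7 years = Nov 2017, and the first 10-year visits at Nov 2007 + 10 years = Nov 2017. The consent wording suggests that criterion 2 was written late. It does not date section 2.2, and nothing in the documents says that results had been looked at by bearing.

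**The case for a change.** The best case for a change is that permission at reporting time is not prespecification. The title raises the question of bearings, one sentence in section 2.2 would settle that they are reported, and the sentence could carry a caveat that bearing was not allocated by the study. The cost is a few tables, and the present wording would allow the same tables without the caveat.

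The textual part stands: section 2.2 permits by-bearing summaries and does not promise them. The caveat is also a fair point of reporting practice. The rest carries less weight. If the text is as late as the consent wording suggests, a stratum added now would not be prospective, and only a disclosure of what had been seen would help. Whether bearing type was recorded cannot be established, because the documents do not list the variables collected. Fixed side-by-side tables would also invite the confounded comparison that a non-comparative study avoids.

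**Conclusion.** No change follows. This is a detail that analysts can fill sensibly under the existing subgroup clause, and a report writer with this title in front of them has an obvious reason to do so. The planned cup-level summaries meet the stated objectives, no test or error rate is involved, and no stated figure depends on the point.

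The most that could be lost is description of the less-used bearing, within a logical limit of p/s. Its practical size cannot be judged, because the removal proportion and the bearing split are not given. If the bearings perform alike, nothing is lost. The conclusion rests on reading the objectives and section 2.1 as setting the target at cup level, and on taking sex in section 2.2 as an example only. It would need another look if the documents set an objective for each bearing or a comparison between them; they do neither.
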